8.1.3 Logistic Regression

Logistic regression will be used to analyse the relationship between binary endpoints and behavioural strategies. The binary endpoints will be the response variables at Months 3, 6, 12 and 24 and PSC total score and the 5 domains of the CSQ will be fitted as a continuous, independent variables in separate univariate models. Estimates for the odds ratio's (OR's), confidence intervals (CI's) and p-values will be presented.

Reference code for logistic regression:

```
ODS OUTPUT oddsratios = _out1 parameterestimates = _out2;
PROC LOGISTIC DATA = <data>;
  MODEL <binary endpoint at visit> = <behavioural endpoint at visit>;
  RUN;
  ODS OUTPUT CLOSE;
```

Where ODS OUTPUT option odds ratios selects the OR's and CI's, and parameter estimates can be used to select the p-value.

The association between baseline PCS total score (<20 vs ≥ 20) and baseline characteristics will also be explored using a logistic regression. A univariate analysis will first be performed with a significance level set at 10%. All significant characteristics will be put forward into a multivariate model. A backward selection will be used to remove

characteristics from the multivariate model which do not have a significant p value at the 5% level.

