6.1.1.2.3 LDA

Low Disease Activity (LDA) is a binary endpoint and can be assessed in four different ways using DAS28-4 ESR, DAS28-4 CRP, SDAI and CDAI. The individual criteria for the four different ways of measuring LDA are:

- DAS28-4 ESR ≤ 3.2
- DAS28-4 CRP ≤ 3.2
- SDAI ≤ 11
- CDAI ≤ 10

Each criteria will be analysed separately.

All of the LDA factor individual components are collected at all visits (Inclusion visit, V1, V2, V3, V4, V5, V6 and any additional visits in the case of discontinuation of Tofacitinib).

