6.1.1.2.9 ACR-EULAR 2011 Boolean Criteria

The America College of Rheumatology-European League Against Rheumatism (ACR-EULAR) 2001 Boolean criteria is derived as:

$$\text{ACR_Remission} = 1, \text{ if } \text{SJC} \leq 1, \text{ TJC} \leq 1, \text{ CRP} \leq 1 \text{ mg/dL, and } \text{PtGA} \leq 1 \text{ cm}$$

$$\text{ACR_Remission} = 0, \text{ Otherwise.}$$

Where CRP is measured in mg/dL.

The proportion of patients which meet the ACR-EULAR 2011 Boolean criteria at Visit X is then calculated as:

No. of patients with ACR-EULAR met at Visit X / Total Number of patients with non-missing ACR-Eular at Month X.

The individual factors of ACR-EULAR 2011 Boolean Criteria are collected at all visits (Inclusion visit, V1, V2, V3, V4, V5, V6 and any additional visits in the case of discontinuation of Tofacitinib).

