8.2 STATISTICAL ANALYSES

All analyses will be performed in the statistical software SAS 9.3 (or higher), unless otherwise specified.

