8.2.6.1 Behavioural Strategies – PCS and CSQ

The impact of behavioural strategies (PCS total score and 5 domains of the CSQ) on Tofacitinib drug survival will be analysed, using three multivariate Cox PH models as described in Section 8.1.1.1 Cox Proportional Hazards.

PCS (individual domain scores and total scores) and CSQ (individual domain scores) will also be summarised as continuous variables as per Section **Error! Reference source not found.** PCS total score will also be summarised as a dichotomous variable (<20 vs ≥ 20) as per Section **Error! Reference source not found.**

Correlations between the behavioural strategies (PCS total score and 5 domains of the CSQ) and each of the endpoints listed below will be investigated as outlined in Section **Error! Reference source not found.**, for the endpoints seen in Figure 3:

- DAS28-4 ESR
- DAS28-4 CRP
- TJC
- SJC
- Duration of morning stiffness
- GIRERD Questionnaire
- EuroQoL EQ-5D-3L
- SF-12v2 Questionnaire
- FACIT-Fatigue Questionnaire
- DAS28 (EULAR Criteria)
- Pain

Figure 3 Timepoints for correlation analyses

Behavioural Strategies Timepoint	Effectiveness Endpoint Timepoint
M0 (Baseline)	M3
M0 (Baseline)	CFB to M3 (M3-M0)
M3	M3
M3	CFB to M3 (M3-M0)
CFB to M3 (M3-M0)	M3
CFB to M3 (M3-M0)	CFB to M3 (M3-M0)
M0 (Baseline)	M6
M0 (Baseline)	CFB to M6 (M6-M0)
M6	M6
M6	CFB to M6 (M6-M0)
CFB to M6 (M6-M0)	M6
CFB to M6 (M6-M0)	CFB to M6 (M6-M0)
M0 (Baseline)	M12
M0 (Baseline)	CFB to M12 (M12-M0)
M12	M12
M12	CFB to M12 (M12-M0)
CFB to M12 (M12-M0)	M12
CFB to M12 (M12-M0)	CFB to M12 (M12-M0)
M0 (Baseline)	M24
M0 (Baseline)	CFB to M24 (M24-M0)
M24	M24
M24	CFB to M24 (M24-M0)
CFB to M24 (M24-M0)	M24
CFB to M24 (M24-M0)	CFB to M24 (M24-M0)

M = Month. CFB = Change from baseline.

Logistic regression will be considered to assess the relationship between behavioural strategies (PCS total score and 5 domains of the CSQ) and each of the binary endpoints listed below as outlined in Section **Error! Reference source not found.**, with a separate model created for each of the timepoints seen in Figure 4:

- LDA
- Patients in remission
- FiRST Questionnaire

Figure 4 Timepoints for logistic regression

Behavioural Strategies Timepoint	Effectiveness Endpoint Timepoint
M0 (Baseline)	M3
M3	M3
CFB to M3 (M3–M0)	M3
M0 (Baseline)	M6
M6	M6
CFB to M6 (M6–M0)	M6
M0 (Baseline)	M12
M12	M12
CFB to M12 (M12–M0)	M12
M0 (Baseline)	M24
M24	M24
CFB to M24 (M24–M0)	M24

M = Month. CFB = Change from baseline.

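### The SAP's reference PROC LOGISTIC code names no event level, so with the stated 1/0 coding of ACR-EULAR remission its odds ratios are for not being in remission

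*SAP*

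**What the plan says.** SAP 8.2 sets the software: "All analyses will be performed in the statistical software SAS 9.3 (or higher), unless otherwise specified". SAP 8.1.3 then gives a short template headed "Reference code for logistic regression". Its procedure statement is "PROC LOGISTIC DATA = <data>" and its model statement is "MODEL <binary endpoint at visit> = <behavioural endpoint at visit>". Neither statement has an EVENT=, REF=, DESCENDING or ORDER= option. The results are to be read directly from the output tables: "Where ODS OUTPUT option odds ratios selects the OR's and CI's, and parameter estimates can be used to select the p-value".

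SAP 8.2.6.1 applies the method to low disease activity, remission and FiRST, at the timepoint pairs listed in its Figure 4: "Logistic regression will be considered to assess the relationship between behavioural strategies" and each of these endpoints.

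On coding, SAP 6.1.1.2.9 sets the ACR-EULAR Boolean remission variable to 1 when all criteria are met and to 0 otherwise. SAP 6.1.1.2.3 says only that "Low Disease Activity (LDA) is a binary endpoint". SAP 6.1.1.2.8 lists the other four remission definitions as thresholds, and SAP 6.1.2.1 gives the FiRST rule as 5 positive items of 6. None of these three sections gives a numeric code for the derived variable.

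**The concern.** An odds ratio has no direction until the modelled level is fixed. The SAP names that level neither in its text nor in its code, so the software default decides. For the one endpoint with a stated code, the default selects the level opposite to the one a reader would expect.

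The models serve a named secondary objective, the relation between behavioural strategies and effectiveness (protocol section 8, SAP 2.4). Direction is the substance of that objective: does more catastrophising go with less remission? A reciprocal odds ratio read as an odds ratio for remission would answer the question the wrong way round. The p-value would be the same in both cases, and neither of the two output tables captured by the code is planned to show which level was modelled.

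**Working it through.** The plan gives no figure to reproduce here. The check covers the code, the algebra and the number of models.

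**1. Code.** The response carries no EVENT= or REF=, and the procedure statement carries no DESCENDING or ORDER=. For a binary response PROC LOGISTIC then models the first ordered level. This is standard behaviour of the named software; the documents do not state it. With 1/0 coding the first ordered level is 0.

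**2. Effect of modelling the other level.** Let p be the probability of remission and logit(p) = a + bx. Then logit(1 - p) = -a - bx. The slope changes sign and its standard error does not, so:
- odds ratio: exp(-b) = 1/exp(b). A true 0.80 becomes 1/0.80 = 1.25; 0.90 becomes 1.11; 0.67 becomes 1.49.
- confidence limits: each is inverted and the two change places.
- p-value: unchanged.

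**3. Illustration on simulated data.** Assumptions: n = 300; a PCS-like score drawn from a normal distribution with mean 20 and SD 11, limited to 0-52; true intercept 0.6 and slope -0.04 per point.

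| Modelled level | OR per point (95% CI) | OR per 10 points (95% CI) | p |
|---|---|---|---|
| 1 (endpoint met) | 0.953 (0.929-0.977) | 0.618 (0.480-0.795) | 0.000185 |
| 0 (endpoint not met) | 1.049 (1.023-1.076) | 1.618 (1.257-2.083) | 0.000185 |

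The second row is the reciprocal of the first, to rounding. The models were not fitted in SAS, so the table shows the algebra and does not test the default.

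**4. Number of models.**
- Endpoints: 4 definitions of low disease activity (SAP 6.1.1.2.3) + 5 of remission (SAP 6.1.1.2.8) + FiRST = 10. Coding is stated for 1 of them.
- Timepoint pairs in Figure 4: 3 per month x 4 months (3, 6, 12, 24) = 12.
- Scores, each in its own model (SAP 8.1.3): PCS total + 5 CSQ domains = 6.
- Documented coding: 1 x 12 x 6 = 72 models.
- Upper bound: 10 x 12 x 6 = 720 models.

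**5. Dependence on coding.** Text values No/Yes give the same inversion, because No sorts first. Coding of 1 = yes and 2 = no would give none. If the endpoints were coded in different ways, some odds ratios in the same grid would be inverted and others not.

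**6. Baseline PCS model.** SAP 8.1.3 and 8.2.6.5 also plan a logistic model for baseline PCS below 20 versus 20 or more. No coding and no event level are given. If it is coded 0/1 with 1 for the high group, the default models low catastrophising.

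**The case against.** The strongest reply has five parts.

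- **It is a template.** The SAP calls it reference code, it contains placeholders, and it mainly shows which output tables to use. A programmer may add the option. This stands as a limit on the claim: the code is not binding line by line. But nothing in the SAP tells the programmer to add anything.
- **The coding is mostly unstated.** A reader might infer that every odds ratio in the grid will be reversed. The documents do not support that, because they give a 1/0 code for one endpoint of ten. This stands in full, and 720 is a maximum under an assumption.
- **The labels are not visible.** A reader might also infer that published tables will be mislabelled. Table shells are in a separate document (SAP section 9), and an odds ratio for the complementary level is not wrong if labelled as such. This stands too: the error arises only if the result is read as being for achieving the endpoint.
- **Other outputs would expose it.** SAP 8.2.6.1 also correlates the same scores with DAS28 at the same months. This helps less than it seems. A higher DAS28 is worse, so a positive correlation of PCS with DAS28 should go with an odds ratio for remission below 1. An inverted odds ratio above 1 looks superficially consistent with the positive correlation.
- **The stakes are secondary.** SAP section 4 says the study has no formal hypotheses, and the primary analysis is a Cox model. This stands and limits the severity.

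**Conclusion.** The point holds in a conditional form. Run as written in SAS, the reference code gives odds ratios for not being in ACR-EULAR remission, each the reciprocal of the odds ratio for remission, with the same p-value. That covers 72 models with documented coding. It extends to as many as 720 only if the other nine binary endpoints are coded 1/0 or No/Yes.

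The conclusion rests on the SAS default for a binary response, on the code being used without an added option, and on readers taking the odds ratios as being for achieving the endpoint. Apart from any software default, the SAP does not define the direction of these odds ratios, and it should. The primary Cox analysis, all p-values and any selection based on p-values are unaffected. The correction should be made before the secondary analyses are run, but the point does not threaten the study's main result.

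**What to change.** Four changes to the SAP:

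1. State that every binary endpoint (each definition of low disease activity, each definition of remission, and FiRST) is coded 1 = criterion met, 0 = not met. This has to come first, because naming level 1 as the event presupposes the coding.
2. In SAP 8.1.3, add `(EVENT='1')` directly after the response variable, so that the line has the form `MODEL endpoint(EVENT='1') = score;`, keeping the existing placeholders.
3. State in words that the odds ratios are for achieving low disease activity or remission, or for a positive FiRST, and check that the table shells say the same.
4. For the baseline PCS model in SAP 8.1.3 and 8.2.6.5, name PCS of 20 or more as the modelled event and give its coding.

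The cost is one code option and a few sentences. No data, power or analysis is lost.

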8.1.4 Analysis of Continuous Data

Continuous data will be summarised in terms of mean, standard deviation (SD), median, first and third quartiles, and minimum and maximum for each visit. Additionally the number of patients with evaluable records for each visit will be presented. Change from baseline tables will be produced for continuous data for each post-baseline timepoint, and will be calculated as per Section 6.1.

8.1.5 Analysis of Categorical Data

Categorical data will be presented as the number of patients and the percentage of patients within a group, based on the number of patients with non-missing data at each visit. These will be presented for each visit.

8.1.6 Analysis of Binary Endpoints

Binary data will be presented using counts and percentages for each visit. Percentages will be calculated based on the number of subjects with a non-missing data at the visit.

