9.5. Sample size

The primary objective of this study is to identify factors predictive of drug survival. This will be investigated using a multivariate Cox regression model. A review of the literature suggests that such an analysis requires at least 10 events (discontinuation of treatment) per variable proposed in a multivariate regression model⁽⁴⁸⁾. The minimum number of subjects to include in the study can then be estimated using the following formula:

$$N = 10 k / p$$

Where p is the smallest of the proportion of positive cases (cases that reached the endpoint) and negative cases (cases that did not reach the endpoint) in the population and k the number of predictor variables.

Assuming a drug survival of 50% at 24 months⁽²⁴⁾ and also that 30% of the potential predictive factors will pass the univariate selection, it will be necessary to observe 150 events (i.e. 50 x 0,3 variables x10 events) in approximately 300 patients (i.e. 150 events/0.50).

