8.2.6 Secondary Analyses

All secondary analyses will use the FAS. Secondary analyses will consider Tofacitinib Total as the treatment group. Summaries of secondary endpoints will be presented for Tofacitinib total, Tofacitinib as monotherapy and Tofacitinib as combination, using the treatment labels seen in Section 2.3.

Each endpoint will apply the specific rules for missing data as described in Section 7 but if there are missing data points after this, no missing data methods will be used to impute data for the secondary analyses.

All the analyses described hereafter in this section will be performed on all assessments collected before permanent Tofacitinib discontinuation (On-Treatment Analysis). In addition, analyses described in sub-sections 8.2.6.2, 8.2.6.3, 8.2.6.4 and 8.2.6.5 will be re-run on all available data including retrieved dropout data (Analysis on All Available Data).

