8.2.6.4 Analysis of Binary Variables

Binary secondary endpoints will be presented as per Section **Error! Reference source not found..** The binary secondary endpoints are:

- LDA
- Patients in remission
- FiRST Questionnaire

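### Neither planned summary of LDA, remission or EULAR response gives the share of starters who are still on tofacitinib and in response

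*SAP*

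**What the plan says.** The denominator rule for binary endpoints is in SAP 8.1.6: "Percentages will be calculated based on the number of subjects with a non-missing data at the visit". SAP 8.2.6.4 applies it to LDA, to "Patients in remission" and to the FiRST result. SAP 6.1.1.2.9 repeats it for Boolean remission, dividing by the "Total Number of patients with non-missing ACR-Eular at Month X". SAP 8.1.5, which SAP 8.2.6.3 uses for EULAR response, also bases percentages on patients with data at the visit.

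SAP 8.2.6 sets which assessments enter. The secondary analyses are to be "performed on all assessments collected before permanent Tofacitinib discontinuation (On-Treatment Analysis". In addition, sections 8.2.6.2 to 8.2.6.5, which contain LDA, remission and EULAR response, "will be re-run on all available data including retrieved dropout data (Analysis on All Available Data". Beyond the rules specific to each endpoint, "no missing data methods will be used to impute data for the secondary analyses".

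No section counts discontinuation as non-response. SAP 6.1.1.2.10 names a non-evaluable category for EULAR response, but no rule says who belongs in it. SAP 5.1 restricts the Full Analysis Set (FAS) to eligible, treated patients with post-baseline measurements.

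**The concern.** Evaluating effectiveness is a stated secondary objective, and Protocol 9.1.6.2 defines the LDA and remission endpoints as percentages of patients, with no restriction to those who stay on the drug. Protocol section 7 describes retention as a marker of treatment success that depends partly on efficacy and safety. If patients stop partly because treatment failed, the on-treatment percentage is taken over a group selected for doing well, and it can climb from visit to visit without anyone improving.

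The rerun widens the group but changes the question. A patient who stopped and responded to a later biologic or targeted synthetic DMARD counts as a responder. A reader who wants to know how many starters are still on tofacitinib and in LDA at month 12 or 24 finds that share in neither output.

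**Working it through.** **Inputs from the documents.** Protocol 9.5: 50 candidate factors, 30% of them passing univariate selection, 10 events per variable, 50% drug survival at 24 months. SAP Table 9: the month-24 window opens at Day 640, with target day 731.

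**Inputs assumed.** On-drug response, response among stoppers, retrieval of stoppers and missingness. The documents give none of these.

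**Step 1: reproduce the planning figure.** Variables = 50 × 0.3 = 15. Events = 15 × 10 = 150. N = 150 / 0.50 = 300. This matches the protocol ("Assuming a drug survival of 50% at 24 months"; "it will be necessary to observe 150 events"). On drug at 24 months: 300 × 0.50 = 150.

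**Step 2: allow for the window.** With a constant discontinuation hazard (assumption), the share on drug at Day 640 is 0.5^(640/731) = 0.545, or about 164 of 300. The on-treatment denominator at month 24 is then about 50–55% of starters before missing data. With 10–20% of 150 on-drug patients unassessed, it is 120–135.

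**Step 3: from on-treatment percentage to share on drug and in LDA.** Share = on-drug percentage × retention.
- 60% on drug, 50% retention: 0.60 × 0.50 = 30%.
- 60% retention: 0.60 × 0.60 = 36%. 70% retention: 0.60 × 0.70 = 42%.
- At 50% retention, on-drug rates of 40%, 50% and 70% become 20%, 25% and 35%.

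**Step 4: can the percentage rise with nobody improving?** Take the extreme case in which the same 90 patients are in LDA at every visit and every stopper is a non-responder. Numbers on drug follow the constant hazard.

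| Visit | On drug | On-treatment LDA | Share of 300 |
|---|---|---|---|
| Month 3 | 275 | 90/275 = 33% | 30% |
| Month 6 | 252 | 90/252 = 36% | 30% |
| Month 12 | 212 | 90/212 = 42% | 30% |
| Month 18 | 178 | 90/178 = 51% | 30% |
| Month 24 | 150 | 90/150 = 60% | 30% |

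**Step 5: the rerun.** Keep 90 of 150 on-drug patients in LDA.
- All 150 stoppers retrieved, 40% in LDA: (90 + 60)/300 = 50%.
- 80% retrieved (120 patients), 20–40% in LDA: (90 + 24)/270 = 42% to (90 + 48)/270 = 51%.

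**Step 6: when is 60% too favourable for all starters?** If stopping counts as failure, the gap is 60 − 30 = 30 points. If instead LDA counts whatever the treatment, the share is 0.5 × 60% + 0.5 × q, where q is the LDA rate among stoppers. The gap is 20 points at q = 20%, 10 points at q = 40%, and 0 at q = 60%.

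**The case against.** Three stronger readings are tempting, and the documents do not support them.

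- A reader might infer that the on-treatment version is the main analysis. The SAP names two analyses and ranks neither; one is listed first and the other is added. The rerun answers a legitimate question of its own: response after starting tofacitinib, whatever followed.
- A reader might infer that the planned percentages overstate effectiveness. As a description of patients remaining on drug with data, the on-treatment figure is valid. Step 6 shows no gap if stoppers reach the same LDA rate and stopping is not itself counted as failure. The documents give no response rate for either group.
- A reader might infer that month 24 will describe half of the starters. That 50% is a planning assumption, and the early opening of the window moves it to about 55% under a constant hazard.

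It is also fair to say that retention is not hidden. It is the primary endpoint, with Kaplan–Meier estimates at 12 and 24 months, and SAP 8.2.1 reports patient numbers at each time point and lists later treatments. SAP 8.1.6 gives counts as well as percentages, so a reader could divide by the FAS size. Nor does a stopper vanish at once: SAP 2.2 asks for data close to discontinuation, and with the wide windows a last on-drug assessment can still count at that visit.

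What remains is that the combined share is left for the reader to build, and a hand calculation cannot separate stoppers from on-drug patients without an assessment or from patients whose drug status is unknown. The objection also limits the remedy. Visits and tests are not mandated, so missing components may be common, and a row that counts every gap as failure could understate response.

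**Conclusion.** The point holds as a gap in reporting. Both planned analyses are valid for their own questions, but neither gives the share of starters who are on tofacitinib and in LDA, remission or EULAR response, although the protocol words the LDA and remission endpoints as unrestricted percentages of patients.

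The size depends on retention. An assumed 60% LDA on drug corresponds to 30% on drug and in LDA at the planned 50% drug survival, and to 36–42% at 60–70%. The on-treatment figure is too favourable for starters only if stopping counts as failure or if stoppers do worse than continuers. The second is plausible where stopping follows treatment failure, but the documents do not show it. These endpoints are secondary and descriptive, so the primary analysis, the sample size and the error rates are untouched.

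**What to change.** Keep both planned analyses. Label the first 'among patients remaining on tofacitinib with data' and print n/N at every visit.

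For LDA, remission and EULAR response, add one supplementary row per visit, 'on tofacitinib and in response':
- The denominator is all FAS patients whose visit window has been reached.
- Recorded permanent discontinuations count as not in response.
- Two groups are shown as separate categories: (a) on drug with no assessment, and (b) lost to follow-up or withdrawn with drug status unknown. SAP 6.1.1.1 censors group (b), so they are not recorded stoppers.
- The row gives the range from (a) and (b) counted as non-response to (a) and (b) excluded from the denominator. For example, take 150 stoppers, 30 on drug but unassessed, and 72 of the remaining 120 in LDA: 72/300 = 24% to 72/270 = 27%. The lower end is a bound; the upper end is not.
- A footnote gives the number of treated patients left out of the FAS for lack of post-baseline data.

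Discontinuation dates and reasons are already collected, so no new data are needed. The cost is SAP wording and one row per endpoint. The added figure will be less favourable than the on-treatment one, and is a lower bound when on-drug data are missing and counted as non-response. It should therefore stand beside the planned rows and not replace them.
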